7.4.2 Model diagnostics

In order to check the validity of assumptions used in the primary efficacy and effectiveness analysis models, model diagnostics will be performed as follows:

- Residuals from the primary model will be checked for normality using a Q-Q plot.
- Variance homogeneity across treatment groups, potential outliers and leverage points will be inspected using descriptive statistics and graphical methods.

These analyses will be reported in Section 16.1.9.2 of the trial report.

7.5 SECONDARY ENDPOINTS

7.5.1 Key secondary endpoints

- 7.5.1.1 Rate of symptomatic hypoglycaemic AEs with confirmed plasma glucose <54 mg/dL and/or severe hypoglycaemic events confirmed by adjudication

Confirmatory analysis

The analysis of the rate of symptomatic hypoglycaemic AEs with confirmed plasma glucose <54 mg/dL and/or severe hypoglycaemic events confirmed by adjudication will utilise a negative binomial model, with terms for treatment, continuous baseline rate, continuous baseline HbA_{1c}, continuous baseline eGFR and pre-existing insulin therapy as fixed effects and log(time at risk) as an offset. The results will be presented as a rate per patient-year. This analysis will be performed on the FAS (OC).

The baseline rate of symptomatic hypoglycaemic AEs with confirmed plasma glucose < 54 mg/dL and/or severe hypoglycaemic events confirmed by adjudication will be calculated based on the event rate during the 4 weeks prior to randomisation, see [section 6.7](#).

The analysis of the rate from Week 5 to Week 26 will include all on-treatment events from the start of Week 5 (Day 29) until the Week 26 cut-off date (as defined in [section 6.1](#)). This period will also define the time at risk.

The analysis of the rate from Week 1 to Week 26 will include all on-treatment events from the date of first study drug intake until the Week 26 cut-off date (as defined in section 6.1). This period will also define the time at risk.

7.5.1.2 Change from baseline in body weight (kg) after 26 weeks

Confirmatory analysis

The analysis of change from baseline in body weight after 26 weeks will follow the strategy for the primary endpoint, MMRM. The model will include the fixed categorical effects of treatment, pre-existing insulin therapy, week and treatment by week interaction, as well as the continuous, fixed covariates of baseline HbA_{1c}, baseline eGFR, baseline body weight and baseline body weight by week interaction. This analysis will be performed on the FAS (OC), including all available on-treatment data up to the Week 26 timepoint.

A descriptive statistics table will present body weight (kg) and body weight change from baseline over time on the FAS (OC, OC-AD).

The treatment response over the treatment period will be illustrated on the FAS (OC) for each visit by plotting the adjusted means (SE) for change from baseline in body weight (kg) at each visit based on the MMRM model. A similar graphic will be created plotting the descriptive mean body weight (kg) at each visit using the FAS (OC).

7.5.1.3 Change from baseline in CGM endpoints after 26 weeks

Confirmatory analysis

The change from baseline in the percentage of time spent in target glucose range as determined by CGM after 26 weeks will be analysed using an ANCOVA model. The statistical model will be:

% time in target range change from baseline = overall mean + continuous baseline HbA_{1c} + pre-existing insulin therapy + continuous baseline eGFR + treatment + continuous baseline % time in range + random error

Treatment and pre-existing insulin therapy are fixed classification effects and baseline HbA_{1c}, baseline eGFR and baseline % time in target range are linear covariates. The random error is assumed to be normally distributed with mean 0 and unknown variance σ^2 .

This analysis will be performed on the FAS (OC-P). All evaluable on-treatment data will be used.

The Week 26 value used for the analysis of change from baseline will be derived from the evaluable data from Week 23 to Week 26. Patients who do not have evaluable data at both Baseline and Week 26 will be excluded from the analysis. See [section 5.4.4](#) for details.

A descriptive statistics table will present time in target range (%) and time in target range change from baseline at week 26 on the FAS (OC, OC-P).

The change from baseline in IQR (mg/dL) as determined by CGM after 26 weeks will be analysed using a similar ANCOVA model, replacing % time in target range with IQR.

7.5.1.4 Change from baseline in total daily insulin dose (U/kg) after 26 weeks

Confirmatory analysis

The analysis of change from baseline in total daily insulin dose after 26 weeks will follow the strategy for the primary endpoint, MMRM. The model will include the fixed categorical effects of treatment, pre-existing insulin therapy, week and treatment by week interaction, as well as the continuous, fixed covariates of baseline HbA_{1c}, baseline eGFR, baseline total daily insulin dose and baseline total daily insulin dose by week interaction. This analysis will be performed on the FAS (OC), including all available on-treatment data up to the Week 26 timepoint.

The baseline total daily insulin dose will be calculated based on the mean daily insulin requirement during the run-in period (Visit 5 to Visit 6). The total daily insulin dose will be calculated for each visit, based on the mean daily insulin requirement over the 14 days prior to the visit (excluding the day of the visit). If <4 days of valid insulin data is available, the visit value will be set to missing. The source data for the total daily insulin dose is the e-diary and this does not undergo a cleaning process. For data handling rules, see [section 5.4.6.2](#).

A descriptive statistics table will present total daily insulin dose (U/kg), total daily insulin dose absolute change from baseline and total daily insulin dose relative change from baseline over time on the FAS (OC, OC-AD).

The treatment response over the treatment period will be illustrated on the FAS (OC) for each visit by plotting the adjusted means (SE) for change from baseline in total daily insulin dose (U/kg) at each visit based on the MMRM model. A similar graphic will be created plotting the descriptive mean total daily insulin dose (U/kg) at each visit using the FAS (OC).

7.5.1.5 Change from baseline in blood pressure after 26 weeks

Confirmatory analysis

The analysis of change from baseline in blood pressure after 26 weeks will follow the strategy for the primary endpoint, MMRM. The model will include the fixed categorical

effects of treatment, pre-existing insulin therapy, week and treatment by week interaction, as well as the continuous, fixed covariates of baseline HbA_{1c}, baseline eGFR, baseline blood pressure and baseline blood pressure by week interaction. This analysis will be performed on the FAS (OC), including all available on-treatment data up to the Week 26 timepoint.

A descriptive statistics table will present blood pressure (mmHg) and blood pressure change from baseline over time on the FAS (OC, OC-AD).

The treatment response over the treatment period will be illustrated on the FAS (OC) for each visit by plotting the adjusted means (SE) for change from baseline in blood pressure (mmHg) at each visit based on the MMRM model. A similar graphic will be created plotting the descriptive mean blood pressure (mmHg) at each visit using the FAS (OC).

All analyses will be performed separately for SBP and DBP.

7.5.2 (Other) Secondary endpoint(s)

This section is not applicable as no secondary endpoints have been specified in the protocol.

7.7 EXTENT OF EXPOSURE

A descriptive statistics table with mean, SD, median and range of the number of days a patient was on treatment will be provided for the treated set. The tables will also provide the sum of the total time (in years) that all patients pooled together were on each treatment.

A separate listing will be created of any patients that switched treatment at any time indicating exposure to each treatment.

A frequency table of number and percent of patients belonging to each categorical range of exposure weeks will be provided:

> 0 to 4 weeks, > 4 to 8 weeks, > 8 to 16 weeks, > 16 to 24 weeks, > 24 to 32 weeks, > 32 to 40 weeks, > 40 to 46 weeks, > 46 to 54 weeks, > 54 weeks. Note that "> 4 to 8 weeks" stands for 29 to 56 days.

In addition, the following exposure cumulative categories will be provided:

For the analysis at week 26, the following exposure cumulative categories will also be provided: ≥ 1 day, ≥ 1 week, ≥ 4 weeks, ≥ 8 weeks, ≥ 16 weeks, ≥ 24 weeks, ≥ 28 weeks. Note that " ≥ 1 week" category refers to 7 days.

For the analysis at week 52, the following exposure cumulative categories will also be provided: ≥ 1 day, ≥ 4 weeks, ≥ 8 weeks, ≥ 16 weeks, ≥ 24 weeks, ≥ 32 weeks, ≥ 40 weeks, ≥ 46 weeks, ≥ 54 weeks.

7.8 SAFETY ANALYSIS

All safety analyses will be performed on the treated set, except one hypoglycaemia analysis that will also be performed on the FAS for a sensitivity purpose (refer to [section 7.8.1.5](#)).

The safety analysis will be primarily performed up to 26 weeks of treatment, and then repeated up to 52 weeks of treatment.

7.8.1 Adverse events

AEs will be coded using the latest version of the MedDRA coding dictionary at database lock.

Any clinically significant new finding in the physical examination, vital signs (pulse symptoms) and in the 12-lead ECG starting after visit 6 (randomisation visit) will be considered as an AE and will be reported as such.

Unless otherwise specified (refer to [section 7.8.1.4](#) for analysis on number of hypoglycaemia events, and respectively to Section 7.8.1.5 for analysis on number of DKA events) the analyses of adverse events will be descriptive in nature and analyses of AEs will be based on the number of patients with AEs (not the number of AEs).

For analysis of AE attributes such as duration, severity, etc. multiple AE occurrence data on the CRF, will be collapsed into AE episodes provided that all of the following applies:

- The same MedDRA lowest level term was reported for the occurrences.
- The occurrences were time-overlapping or time-adjacent (time-adjacency of 2 occurrences is given if the second occurrence started on the same day or on the day after the end of the first occurrence).
- In addition certain analyses (other than the general analyses by SOC and PT produced by the XAE macro) will have their own collapsing rules. This concerns the following endpoints:
 - Genital infection events will not be collapsed if they are representative of different types (i.e. fungal balanitis or vulvovaginitis versus other than fungal balanitis or vulvovaginitis);
 - Sepsis events will not be collapsed if they are representative of different sources of infection (i.e. urinary tract (urosepsis) versus other than urinary tract);
 - Severe hypoglycaemia endpoint confirmed by adjudication will not be collapsed;
 - Hypoglycaemia adverse events will not be collapsed (except in case of occurrences with identical onset date, time and glucose value);
 - Lower limb amputation endpoint will not be collapsed
- Treatment did not change between the onset of the occurrences OR treatment changed between the onset of the occurrences, but no deterioration was observed for the later occurrence.

For further details on summarization of AE data, please refer to [\(8\)](#).

7.8.1.1 Assignment of AEs to treatment

In general, the analysis of adverse events will be based on the concept of treatment emergent adverse events.

This means that all adverse events occurring between first drug intake until 7 days after last drug intake will be assigned to the randomised treatment. All adverse events occurring before first drug intake will be assigned to 'screening' and all adverse events occurring after last drug intake + 7 days will be assigned to 'post-treatment'. For details on the treatment definition, see [section 6.1](#).

For all adverse event analyses at week 26 except the specific analyses on hypoglycaemia (i.e. not the general hypoglycaemia AE analysis by SOC and PT), all adverse events with an onset date up to the minimum of (treatment stop + 7 days) and the week 26 cut-off date will be included. Events occurring after this date will be censored for the week 26 analysis. Refer to Section 6.1 for details on the week 26 cut-off date definition.

For the specific analyses on hypoglycaemia, the events with an onset date up to the minimum of (treatment stop + 1 day) and the week 26 cut-off date will be included.

7.8.1.2 Analysis of other significant AEs

Other significant AEs will be reported and summarised according to ICH E3 criterion. Thus, AEs classified as 'other significant' will include those non-serious and non-significant adverse events with:

- 'action taken = discontinuation' or 'action taken = reduced', or
- Marked haematological and other lab abnormalities or lead to significant concomitant therapy as identified by the Clinical Monitor/Investigator at a Medical Quality Review meeting or Blinded Report Planning Meeting.

7.8.1.3 AE summaries

An overall summary of adverse events will be presented.

The frequency of patients with adverse events will be summarised by treatment, primary system organ class and preferred term. AEs will also be reported by intensity. Separate tables will be provided for patients with other significant adverse events according to ICH E3 (9), for patients with adverse events of special interest (AESI), for patients with serious adverse events, for patients with AEs leading to discontinuation, and for patients with drug-related AEs.

The system organ classes will be sorted according to the standard sort order specified by EMA, preferred terms will be sorted by frequency (within system organ class).

Appendix 16.1.9.2 will include the following analyses:

- an analysis on patients with adverse events by outcome,
- an analysis on the frequency of patients with non-serious adverse events occurring with incidence in preferred term greater than 5 % by treatment for disclosure on clinicaltrials.gov website.

The following analyses will also be reported in Appendix 16.1.9.2 for disclosure on EudraCT:

- AEs per treatment arm

This analysis includes the number of patients with serious AEs, the number of patients with non-serious AEs >5%, the total number of deaths (all causes), as well as the total number of deaths resulting from drug-related adverse events.

- Number of patients with non-serious AEs > 5% within any treatment arm, for each preferred term (grouped by standard SOC terms)
- Number of patients with serious AEs on preferred term level (grouped by standard SOC terms)

7.8.2 Laboratory data

For continuous safety laboratory parameters standardised and normalised values will be derived as well as the differences to baseline. The process of standardisation and normalisation as well as standard analyses for safety laboratory data are described in the BI guidance for the Display and Analysis of Laboratory Data ([10](#)). All analyses considering multiple of times upper limit of normal (ULN) will be based on original and not normalized data.

The analyses of laboratory data will be descriptive in nature and will be based on BI standards.

Results of laboratory analyses will be presented based on both SI units and US conventional units.

Baseline for safety laboratory parameters will be the last available measurement before the start of randomised study drug. In general, laboratory measurements taken up to 3 days after the last administration of randomised study drug will be considered as on-treatment. The exception will be for the liver enzyme elevation analysis (see below).

For all laboratory analyses at week 26, all laboratory parameters measured up to the minimum of (treatment stop + 3 days) and the week 26 cut-off date will be included. Laboratory measures observed after this date will be censored for the week 26 analysis. Refer to [section 6.1](#) for details on the week 26 cut-off date definition.

Only patients with at least one available on-treatment value will be included in the analysis of an individual laboratory parameter. All individual data will be presented in listings.

7.8.2.1 General laboratory evaluation

Laboratory values will be compared to their reference ranges and frequency tables will be provided for the number of patients within and outside the reference range at baseline and the last measurement on treatment. Descriptive statistics will be provided by treatment group for baseline, on-treatment values and for changes from baseline based on normalised values, as well as on the basis of standardized values for parameters with an incomplete reference range (e.g. ALT).

Descriptive statistics will in addition be calculated for the change from baseline in haematocrit over time, including during the follow-up period. In particular, statistics will be provided for last-value on-treatment, follow-up, change from baseline from last on-treatment value and follow-up, and change from last on-treatment assessment to follow-up.

Frequency tables will summarise the number of patients with potentially clinically significant abnormalities as defined for the new XLAB macro (version 2.03) and the criteria for clinically significant abnormalities based on normalised laboratory values will be listed.

7.8.3 Vital signs

Other than the analysis of SBP and DBP as key secondary endpoints, only descriptive statistics are planned for the summary of pulse rate (bpm) and change from baseline in pulse rate over time based on the treated set (OC, OC-AD).

Pulse rate observation measured up to the minimum of (treatment stop + 1 day) and the week 26 cut-off date will be included in the week 26 analysis. Pulse rate observation observed after this date will be censored for the week 26 analysis. Refer to [Section 6.1](#) for details on the week 26 cut-off date definition.

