# 7.3.4 Safety analyses

Safety will be assessed for the endpoints listed in Section 5.1.3.2. All treated patients will be included in the safety evaluation (i.e. in the TS). Safety analyses will be mostly descriptive in nature and will be based on BI standards. In addition, statistical analysis for selected endpoints (to be defined in the TSAP) may be performed, if appropriate. No hypothesis testing is planned.

The active empagliflozin treatment groups will be compared with the placebo group in a descriptive way. Tabulations of frequencies/proportions will be used for the evaluation of

Page 85 of 144

Proprietary confidential information © 2017 Boehringer Ingelheim International GmbH or one or more of its affiliated companies

categorical (qualitative) data, and tabulations of descriptive statistics will be used to summarise continuous (quantitative) data.

Adverse events will be coded using the Medical Dictionary for Drug Regulatory Affairs (MedDRA). The analysis of AEs will be based on the concept of treatment emergent adverse events. That means that all AEs occurring from first study medication intake until 7 days after last study medication intake will be assigned to the randomised treatment. This includes AEs that start before first study medication intake and deteriorate under treatment. All AEs occurring before first study medication intake will be assigned to 'pre-treatment' and all AEs occurring after last study medication intake + 7 days will be assigned to 'post-treatment'. Additional listings based on actual treatment at onset of AE will be produced for patients who receive incorrect treatment at any point during the trial. Specific analyses of hypoglycaemia will assign events only up to the end of the last study medication intake + 1 day to the randomised treatment, later hypoglycaemia events will be assigned to 'post-treatment'.

Frequency, severity, and causal relationship of AEs will be tabulated by system organ class and preferred term after coding according to the current version of the MedDRA.

Independent of this rule, the relationship of an AE to the study medication will be assessed by the Investigator.

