Laboratory data will be analysed both quantitatively as well as qualitatively. The latter will be done via comparison of laboratory data to their reference ranges. Values outside the reference range as well as values defined as clinically relevant will be highlighted in the listings. Treatment groups will be compared descriptively with regard to distribution parameters as well as with regard to frequency and percentage of patients with abnormal values or clinically relevant abnormal values.

Vital signs, physical examinations, or other safety-relevant data observed at screening, baseline, during the course of the trial and at the end-of-trial evaluation will be assessed with regard to possible changes compared to findings before start of treatment.

Page 86 of 144

Proprietary confidential information © 2017 Boehringer Ingelheim International GmbH or one or more of its affiliated companies

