6.6.1.3 Observed cases - all data (OC-AD) analysis

Additionally, it is planned to perform effectiveness analyses including all available data that were observed, i.e. both on- and off-treatment values. Missing data in the analysis will not be replaced. Subsequent handling of missing data will be performed via a likelihood-based method and will use the mixed-effect model repeated measures (MMRM).

For blood pressure endpoints, data after a change in anti-hypertensive therapy will not be excluded.

For CGM endpoints, if both on- and off treatment data are available, OC-AD will consider all measurements in the derivation of the endpoints, regardless of whether on- or off-treatment. For more details of the derivation of CGM endpoints, see [section 5.4.4](#). Additionally, data after the intake of paracetamol will not be excluded from the derivation of the endpoints.

A similar approach will be applied to insulin endpoints if both on- and off-treatment data is available in the 14 days prior to a visit.

For pulse rate, the OC-AD imputation will be used to present descriptive statistics analyses. For blood pressure endpoints, the OC-AD imputation will serve for descriptive statistics and sensitivity analyses.

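### SAP 7.8.3: the Week 26 all-data pulse table cannot hold off-treatment values, and no visible blood pressure descriptive table uses the treated set

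*SAP*

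**What the plan says.** **Pulse rate.** SAP 7.8.3 plans descriptive statistics for pulse and "change from baseline in pulse rate over time based on the treated set (OC, OC-AD". SAP 6.6.1.3 defines OC-AD as using both on- and off-treatment values and assigns it to this endpoint: "For pulse rate, the OC-AD imputation will be used to present descriptive statistics analyses". SAP 7.8.3 then sets the Week 26 rule: "Pulse rate observation measured up to the minimum of (treatment stop + 1 day) and the week 26 cut-off date will be included", followed by "Pulse rate observation observed after this date will be censored for the week 26 analysis". SAP 6.1 defines the Week 26 cut-off. For a patient who stopped before Week 26, it is the earlier of drug stop + X days and the Week 26 visit (or Day 182 if there is no visit in the window).

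**Blood pressure.** Protocol 7.3.4 says all treated patients are "included in the safety evaluation (i.e. in the TS" and lists among the data to be assessed for change from before treatment: "Vital signs, physical examinations, or other safety-relevant data observed at screening, baseline, during the course of the trial". SAP 7.8 places all safety analyses on the treated set, with one hypoglycaemia analysis also run on the FAS. SAP 7.8.3 nevertheless limits its own summary to pulse and refers SBP and DBP to their key secondary analyses: "Other than the analysis of SBP and DBP as key secondary endpoints, only descriptive statistics are planned for the summary of pulse rate". The descriptive table there, in SAP 7.5.1.5, presents values and "blood pressure change from baseline over time on the FAS (OC, OC-AD".

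**The concern.** Two things in one short section do not fit the rest of the plan.

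First, a table labelled OC-AD is meant to show what happens to pulse when patients who have stopped study drug are kept in. If the inclusion rule removes their later values, the table carries the label without the content. A reader comparing the OC and OC-AD tables would see no difference and might conclude that off-treatment values do not matter, when none were used.

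Second, a safety summary of a vital sign should not depend on whether the patient has a usable HbA1c. The FAS imposes that condition and the treated set does not. Protocol 1.2.3.1 reports systolic reductions of up to 4.8 mmHg against placebo in Type 2 diabetes, so the documents themselves give reason to expect this drug to move blood pressure. Pulse and blood pressure are taken together under protocol 5.2.4, yet only pulse is summarised for all treated patients.

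**Working it through.** **Pulse: does the Week 26 rule leave any off-treatment value?**

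Let S be the drug stop day, X the follow-up period in days, and V the Week 26 visit day (182 if no visit falls in the window). For a patient who stops before Week 26:

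- cut-off (SAP 6.1): C = min(S + X, V)
- last day admitted (SAP 7.8.3): L = min(S + 1, C) = min(S + 1, S + X, V)
- a value on day d is off-treatment (SAP 6.7) if d > S + X

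Since L ≤ S + X, no off-treatment value can satisfy d ≤ L. Table 6.7: 1 has no row for pulse (blood pressure has 1 day), so X is open, but the result does not depend on it. An enumeration over stop days 1 to 181 and Week 26 visit days 155 to 210 or missing, with X = 0, 1, 3 and 7, retained 0 values later than S + 1 in every case.

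Patients still on treatment at Week 26 have no earlier off-treatment value to contribute. OC and OC-AD therefore draw on the same observations.

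Example: S = 60, X = 1, V = 182. C = min(61, 182) = 61 and L = min(61, 61) = 61. The planned Week 12, 18 and 26 values (Days 84, 126, 182) all fall after Day 61 and are left out of both tables. Such values should exist, because protocol 6.2.3.4 keeps vital signs among the assessments for patients who have stopped drug.

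The documents give no discontinuation rate. If 10% to 15% stopped before Week 26 (an assumption), up to 240 × 0.10 = 24 to 240 × 0.15 = 36 patients per arm would be affected.

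**Blood pressure: which set is used where?**

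| Source | Data | Set |
|---|---|---|
| Protocol 7.3.4; SAP 7.8 | safety | treated set |
| SAP 7.8.3 | pulse descriptives | treated set |
| SAP 7.5.1.5 | SBP/DBP descriptives | FAS |
| SAP Table 6.3: 1 | SBP/DBP imputation sensitivity analysis | randomised set, with a baseline measurement |

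The treated set needs one dose. The FAS (SAP 6.3) also needs a baseline HbA1c and at least one on-treatment HbA1c, which means within 7 days of drug stop (Table 6.7: 1). In the protocol Flow Chart the first vital signs after randomisation are at Week 1. The first scheduled HbA1c is at Week 4, or at the early end-of-treatment visit. A patient can therefore have a Week 1 blood pressure and no qualifying HbA1c.

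**How many?** Protocol 7.7 gives the only figure. Its calculation reproduces: difference 0.3, SD 0.9, two-sided alpha 0.025 and power 90% give 224.7 by t-test, so 225 per arm. Then 225 / 0.94 = 239.4, rounded up to 240. The allowance is 240 − 225 = 15 per arm, or 3 × 15 = 45 in total (6% of 720 is 43.2). This counts randomised patients outside the FAS for any reason. The documents do not say how many of them would have been treated.

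**The case against.** On pulse, the best defence is that the inclusion sentence was meant as the OC rule only. SAP 7.8.2 has parallel wording for laboratory data, where no OC-AD table is ordered, and SAP 6.6.1.3 specifically assigns OC-AD to pulse. That is a plausible intention, but the text of 7.8.3 states no exemption, and the SAP 6.1 cut-off would impose nearly the same cap anyway. The limit is also stated only for the Week 26 analysis. SAP 7.8 repeats safety up to Week 52 and 7.8.3 gives no corresponding limit there, so off-treatment values, including those at the Week 26 visit, could appear in that repeat. This stands: a reader might infer that off-treatment pulse data are lost from reporting altogether, and the documents do not support that.

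On blood pressure, protocol 7.3.4 prescribes no by-visit SBP and DBP table, and the FAS tables do include OC-AD. Changes in vital signs that the investigator judges clinically relevant are recorded as adverse events (protocol 5.3.7) and analysed on the treated set. Parts of the SAP are also not public. All of this stands. It rules out the inference that blood pressure goes without safety reporting and limits the point to what the visible text plans. It does not supply a treated-set summary of values.

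A reader might also infer that the FAS drops everyone who stops in the first weeks. It does not. The early end-of-treatment visit includes an HbA1c, the 7-day allowance applies, and the Week 4 window opens on Day 2, so a timely visit keeps an early stopper in the FAS.

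**Conclusion.** Both parts hold, at minor severity.

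- The Week 26 OC-AD pulse table, produced as written, holds no off-treatment value and duplicates OC. This follows from the rules alone, whatever value X takes. It concerns the Week 26 analysis only.
- No visible blood pressure descriptive table uses the treated set. Treated patients with no baseline HbA1c or no on-treatment HbA1c are left out, and their number is unknown. The 6% in protocol 7.7 (about 15 per arm) indicates scale only. It is tempting to read it as a maximum number of treated patients missing, but it is a planning estimate that the actual number could exceed, and some of those patients may never have been treated.

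No alpha, power or confirmatory result is affected. The blood pressure part assumes that no treated-set table sits in text withheld from the public SAP; SAP 7.8.3 itself shows no sign of a cut.

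**What to change.** In SAP 7.8.3:

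(a) Apply the treatment stop + 1 day limit to OC only. For OC-AD in the Week 26 analysis, include all pulse values up to the actual Week 26 visit date if it falls within the window, and otherwise up to Day 182. This must replace the SAP 6.1 cut-off for OC-AD, because that cut-off is itself capped at drug stop + X days. If no off-treatment pulse is wanted at Week 26, dropping OC-AD from that table would also remove the contradiction, but SAP 6.6.1.3 would then need to say so.

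(b) Next to pulse, add SBP and DBP, value and change from baseline by visit, on the treated set for OC and OC-AD.

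The cost is one sentence and a few extra descriptive tables. All the data are already collected.
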